3. Record the adverse effects of the different pharmacological therapies reported in the different groups throughout their follow-up.
4. Evaluate the lung function of the different groups at 3 months after discharge, 6 months and 12 months after discharge.

METHODS

a) Location of the study.

National Institute of Respiratory Diseases, Ismael Cosío Villegas México.

Smoking and COPD Research Department.

b) Description of the population:

Inclusion criteria:

1. Over 18 years of age.
2. Active smokers (smoking more than 100 cigarettes in their entire life and having consumed cigarettes in the last 30 days)
3. Hospitalized subjects with acute or chronic lung disease.
4. Signing of informed consent.

Exclusion criteria:

1. Subjects with pharmacological treatment to stop smoking during recruitment or in the last month.
2. Contraindications to the use of pharmacological therapy. (Annex is attached the contraindications for the use of medications)
3. Subjects who cannot maintain follow-up.

Elimination criteria:

1. In an analysis by intention to treat, there will be no elimination of subjects after randomization.

Sample size:

The sample size calculation is carried out by difference between proportions, with a confidence level of 95%, power of 80%, unilateral, with an observed proportion of 65% and an expected proportion of 80% for the combination of pharmacological therapy; 50 subjects are required for each group; If a loss of participants is estimated at 25%, 67 subjects are required for each group. The sample size was carried out in the WinEpi 2006 program.

c) Outcome variables and description of other study variables.

Outcome variable:

-Abstinence: abstinence from tobacco is defined as its suspension 12 months after hospital discharge, corroborated by detection of exhaled carbon monoxide less than 7 ppb and/or detection of cotinine in urine (positive).

-Active smoker: defined as an active smoker who has consumed more than 100 cigarettes in his or her entire life and who has consumed cigarettes in the last 30 days.

-CBT (cognitive behavioral therapy) is a model for treating problematic behaviors that focuses primarily on identifying and changing maladaptive patterns of behavior and thoughts, including problem-solving and coping skills rooted in relapse prevention theory, along with the cognitive restoration of maladaptive thoughts to regulate emotions and is combined with the recommendations of the Clinical Practice Guideline (CPG) for tobacco.

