(14)

-Acute or chronic lung disease: Acute or chronic lung disease will be considered by medical diagnosis.

-Exhaled carbon monoxide: a value greater than or equal to 7 ppb is defined as positive (subject with active smoking).

-Cotinine in urine: defined as positive (subject with active smoking) positive test (qualitative test)

-Nicotine dependence (Fagerström Questionnaire): mild, moderate and severe.

-Withdrawal symptoms questionnaire.

-Nicotine Craving Questionnaire (Urge to smoke, understood as a physiological and motivational state that drives the desire to smoke tobacco).

-Adverse reactions questionnaire.

-Respiratory symptoms questionnaires (PLATINO).

-Pulmonary function tests (pre- and post-bronchodilator spirometry, carbon monoxide diffusion, and 6-minute walk)

-Beck Anxiety and Depression Questionnaires.

Procedures for collecting information using instruments and data quality control methods.

Data Capture.

a)

b) 1-Subject identification (inclusion/exclusion criteria)

c) 2-Signature of informed consent

d) 3-Randomization of the drug (2 groups: a-nicotine patches, b-combination: nicotine patches + bupropion)

e) 4-Start hospitalization treatment

f) - Processes: Medications are given in a personalized way during hospitalization; brief advice is given, and questionnaires and measurements of exhaled CO and cotinine in urine are performed (treatment start day is day 0). The pharmacological treatment given to the subject will be for at least 12 weeks.

g) 5-Monitoring during hospitalization to provide medications

- h) 6-Upon discharge, an appointment is made at the Smoking Clinic within the first 14 days of discharge, and anti-smoking treatment for home use and brief advice will be provided.
- i) 7-First appointment at the Smoking Clinic
- j) - Processes: brief advice; intake of exhaled CO and cotinine in urine). It is scheduled to begin cognitive behavioral therapy (CBT) in a group, which lasts ten sessions, two times a week, with mixed modality (online or in-person).
- k) 8-Start CBT in the next two weeks after discharge.
- l) 9- Second appointment at the Smoking Clinic at the end of therapy (3 months after discharge)
- m) - Processes: brief advice; questionnaires and measurement of exhaled CO and cotinine in urine are performed; pre- and post-bronchodilator spirometry, carbon monoxide diffusion, 6-minute walk.
- n) 10-Third appointment at the Smoking Clinic 6 months after discharge:

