- o) - Processes: brief advice; questionnaires and measurement of exhaled CO and cotinine in urine are performed; pre- and post-bronchodilator spirometry, carbon monoxide diffusion, 6-minute walk)
- p) 11-Fourth appointment at the Smoking Clinic 12 months after discharge
- q) - Processes: brief advice; questionnaires and measurement of exhaled CO and cotinine in urine are performed; pre- and post-bronchodilator spirometry, carbon monoxide diffusion, 6-minute walk)
- r) The information collection will be carried out through the INER RedCAP platform, which has security mechanisms for the data obtained and methods for adequate control. The protocol researchers will carry out data capture.

Results analysis plan.

1- A retrospective analysis was carried out on hospitalized patients with a history of active smoking, with the following characteristics: 40% of the patients evaluated had low dependence on nicotine, and 60% had moderate and severe dependence. Of the patients evaluated, 72% were male, and 28% were female. Proportional allocation is carried out for stratified sampling, Stratified randomization for sex (man and woman), and for low and moderate/severe dependence

2- Statistical analysis methods according to the type of variables: the variables will be analyzed according to their type of distribution and whether they are quantitative or qualitative, by student's t or chi2 as appropriate. A descriptive analysis will be carried out on each of the variables. Subsequently, a comparative analysis will be carried out between the 2 groups included, using ANOVA or Kruskal Wallis, depending on their distribution. The analysis of the main objective will be carried out by intention to treat according to the treatment granted and randomization. Randomization was stratified by level of nicotine dependence and sex. There will be no blinding. The primary outcome will be abstinence at 12 months, and its association with the randomized treatment group will be seen. As a complementary analysis, a per-protocol analysis will be performed according to the treatment received. Finally, through multivariate analysis by logistic regression, abstinence or non-abstinence at one year was analyzed depending on the treatment received, adjusted for the different covariates such as sex, age, smoking rate, and level of dependence.

3-The statistical analysis will be carried out using the STATA V13 statistical package.

ETHICAL CONSIDERATIONS

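### The plan rules out all blinding, so 12-month abstinence may be classified and analysed with the arm known, although open-label treatment does not require this

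*Combined protocol and SAP*

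**What the plan says.** The trial compares two arms (Data Capture, step 3): "2 groups: a-nicotine patches, b-combination: nicotine patches + bupropion". No placebo is mentioned. On masking, item 2 of the Results analysis plan says only "There will be no blinding". It makes no exception for outcome classification, data entry or analysis, and nothing elsewhere describes a masked assessor or a masked analysis.

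On data entry, the last item of the Data Capture list says "The protocol researchers will carry out data capture". The 12-month visit is described in the same list as "brief advice; questionnaires and measurement of exhaled CO and cotinine in urine are performed", followed by the lung-function tests. It does not say who does any of these.

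The primary outcome is given in the Results analysis plan: "The primary outcome will be abstinence at 12 months, and its association with the randomized treatment group will be seen". Under Outcome variables, "abstinence from tobacco is defined as its suspension 12 months after hospital discharge", and this is "corroborated by detection of exhaled carbon monoxide less than 7 ppb and/or detection of cotinine in urine (positive". The separate entry for urine cotinine, a little further on, reads "defined as positive (subject with active smoking) positive test (qualitative test".

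**The concern.** Adding a tablet to a patch without a placebo explains why patients and treating staff know the arm. It does not explain why the person who decides whether a patient counts as abstinent, or the person who runs the comparison, should know it. The plan gives no reason for extending the absence of blinding to those steps.

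This matters most where a step leaves room for judgement, and here several do. The source for tobacco suspension is not named. The two biochemical tests can disagree without a stated tie-break. The statistical methods are chosen as appropriate from a list, and the covariates are given as examples. If such choices lean even slightly towards one arm, the lean enters the primary comparison and looks like a treatment effect.

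**Working it through.** **Step 1. Where is judgement possible?** Outcome variables join CO and cotinine by and/or. Taking a negative cotinine as evidence of abstinence, as the separate cotinine entry implies, the four possible result patterns are classified as follows:

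| CO | Cotinine | Either test suffices | Both tests required |
|---|---|---|---|
| below 7 | negative | abstinent | abstinent |
| below 7 | positive | abstinent | not abstinent |
| 7 or more | negative | abstinent | not abstinent |
| 7 or more | positive | not abstinent | not abstinent |

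The two discordant patterns change with the reading, and the plan does not choose. The abstinence definition adds a further conflict: taken literally, it lets a positive cotinine corroborate abstinence, while the cotinine entry makes a positive result a sign of active smoking. That contradiction must be reconciled in its own right, and masking would not cure it. Until both points are settled, someone has to decide how to code these patients, and nothing in the plan keeps the arm from that person.

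**Step 2. Is there a plan figure to reproduce?** None concerns blinding. The illustration below borrows three figures from the Sample size paragraph: 65% abstinence, 67 per group, and a one-sided 5% test. The 67 follows from the plan's 50 and its 25% loss: 50 / (1 − 0.25) = 66.7, rounded up to 67. Whether 50 is itself right is a separate question that does not affect this point.

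**Step 3. Illustration of size.** The documents give no misclassification rate, so the shift d is an assumption: 2, 3 or 5 percentage points in favour of one arm, with true abstinence p = 0.65 in both arms and n = 67 in each. The recorded rate in the favoured arm is p′ = 0.65 + d, and p̄ is the mean of p and p′.

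- SE₀ = √(2·p̄(1 − p̄)/n)
- SE₁ = √((p(1 − p) + p′(1 − p′))/n)
- One-sided false-positive rate = 1 − Φ((1.645·SE₀ − d)/SE₁)
- Two-sided rate = 1 − Φ((1.960·SE₀ − d)/SE₁) + Φ((−1.960·SE₀ − d)/SE₁)

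For d = 0.05: p̄ = 0.675, SE₀ = 0.0809, SE₁ = 0.0808. The one-sided rate is 1 − Φ(1.028) = 15.2%. The two-sided rate is 1 − Φ(1.344) + Φ(−2.58) = 8.95% + 0.49% = 9.4%.

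| Assumed shift | Patients of 67 | One-sided | Two-sided |
|---|---|---|---|
| none | 0 | 5% | 5% |
| 2 points | 1.3 | 8.1% | 5.7% |
| 3 points | 2.0 | 10.1% | 6.6% |
| 5 points | 3.4 | 15.2% | 9.4% |

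**Step 4. How strong is the assumption?** With 65% truly abstinent, only 35% of an arm (0.35 × 67 = 23 patients) can be wrongly upgraded. A 2-point shift means 0.02/0.35 = 6% of the smokers in one arm are misclassified and none in the other; a 5-point shift means 0.05/0.35 = 14%. If the planned 25% are lost and 50 per arm are assessed, the one-sided rates are 7.6%, 9.2% and 13.3%.

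**The case against.** The strongest answer is that abstinence here is not a bare statement by the patient. It must be corroborated by CO, cotinine or both, which leaves an assessor less room than self-report would. That stands as a limit on the risk. It is weakened, but not cancelled, by the and/or rule and the conflicting cotinine entries.

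A reader might infer more than the documents support on five points:

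- **That researchers who know the arm interview, measure and classify the patients.** The plan says who enters the data, not who asks the questions, takes the readings or decides the outcome. It describes no interview and no repeat CO readings. That suspension is self-reported is a fair inference from its being corroborated, but it is not stated.
- **That the staff doing the lung-function tests could serve as masked assessors at no cost.** The tests are listed at 3, 6 and 12 months, but the documents do not say who performs them. They may be the same researchers.
- **That the inflation above is an estimate.** It rests on an assumed shift. The larger figures also need a one-sided test, and that choice appears only in the Sample size paragraph. The analysis section names chi-squared, which is ordinarily two-sided.
- **That no later analysis could help.** CO and cotinine are recorded at follow-up visits, so a sensitivity analysis on biochemical results alone could address bias from questioning and coding, though not bias in taking the readings.
- **That an unmasked analyst has been shown to bias the result.** The illustration concerns classification only. The primary comparison is a simple two-group test, and fixing the rules in advance would remove much of the analyst's discretion. Coded arms are a cheap supplement to that.

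**Conclusion.** The point holds in a limited form. The plan states a blanket rule that allows the primary outcome to be classified and analysed with the arm known; it is not merely silent on the matter. Open-label treatment does not require this, and the unresolved coding of CO and cotinine gives arm-aware judgement somewhere to act.

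The size is unknown. Under the assumed 2- to 5-point shift, at 65% abstinence and 67 per arm, the false-positive rate would be 8%–15% one-sided or 6%–9% two-sided, against a nominal 5%. This shows that one to three patients can matter in a trial of this size; it does not show that such a shift will occur. The change is worth making because it is cheap and because the plan gives no reason for leaving these steps open. The point does not rest on any claim about who staffs the visits.

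**What to change.** Replace the single sentence on blinding in item 2 of the Results analysis plan with:

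> Patients and treating staff are not blinded. Each patient's 12-month abstinence status is classified by a fixed rule from the recorded smoking-status answer, CO and cotinine, in an export without treatment arm, and the analysis file carries coded arms (A/B) until that status is locked for every patient.

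For the rule to be fixed, the plan must say how discordant CO and cotinine results are classified, and the two cotinine entries must be reconciled, before any 12-month status is assigned. The plan should also state who takes the measurements. Where staffing allows (an assumption, since the documents do not describe it), the smoking-status question, CO and cotinine should be taken by someone not told the arm.

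The cost is a REDCap access setting and a coded export. Masked classification and coded analysis add no visit or test and do not change the sample size. Patients still know their treatment when they report their smoking, and some will reveal it to staff, so the change reduces bias without removing it.

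### The only covariate-adjusted model of 12-month abstinence groups participants by an undefined treatment received, so no adjusted estimate by randomised arm is planned

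*Combined protocol and SAP*

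**What the plan says.** Item 2 of the Results analysis plan describes three analyses of abstinence.

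- **Primary.** "The primary outcome will be abstinence at 12 months, and its association with the randomized treatment group will be seen". The analysis set is given as "The analysis of the main objective will be carried out by intention to treat according to the treatment granted and randomization".
- **Complementary.** "a per-protocol analysis will be performed according to the treatment received".
- **Adjusted.** A logistic regression in which "abstinence or non-abstinence at one year was analyzed depending on the treatment received, adjusted for the different covariates such as sex"; the other covariates named are dependence level, age and smoking rate.

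The same item adds "Randomization was stratified by level of nicotine dependence and sex" and "There will be no blinding".

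On exposure to treatment, Data Capture says (step 4) "The pharmacological treatment given to the subject will be for at least 12 weeks", and (step 6) that at discharge "anti-smoking treatment for home use and brief advice will be provided". Step 5 mentions monitoring in hospital in order to supply the drugs. For the home phase, neither the variable list nor the visit procedures name an adherence measure. They list questionnaires (withdrawal, craving, adverse reactions and others), exhaled CO, urinary cotinine and lung function tests.

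**The concern.** The plan uses two different terms for the grouping variable within one paragraph. The primary contrast uses the randomised group. The regression, which is the only multivariable model in the document and the only one containing the two stratification factors, uses treatment received.

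Both arms use patches and one adds bupropion, so a participant who stops bupropion and keeps the patch looks like a member of the comparator arm. No rule says how that person is classed, or how much treatment counts as received. Stopping happens after randomisation and may depend on how the quit attempt is going. Sex, age, smoking rate and dependence are baseline variables and cannot remove a selection effect of that kind.

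Two things are at stake. The adjusted estimate would differ from the intention-to-treat result in its covariates and in who counts as treated, so a reader could not tell which explains a discrepancy. And because the trial is open-label and the term is undefined, the classification could be settled after outcomes are known.

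**Working it through.** **1. Reading the text.** There is no figure in the plan to reproduce on this point. Setting the sentences of item 2 side by side:

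| Analysis | Grouping named | Adjusted? |
|---|---|---|
| Primary (intention to treat) | randomised group, but also treatment granted | none stated |
| Per-protocol | treatment received | none stated |
| Logistic regression | treatment received | sex, age, smoking rate, dependence |

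No row combines the randomised group with adjustment.

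**2. Inputs for an illustration.** From the Sample size section: 65% abstinence, and 67 per group (50 after the expected 25% loss). Assumed, because the documents give nothing: no true effect, so *p* = 0.65 in both arms; a share *a* of abstainers and a share *s* of smokers in the combination arm stop bupropion.

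**3. Stoppers regrouped as patch only.**

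- Remaining combination group: p(1−a) / [p(1−a) + (1−p)(1−s)]
- Enlarged patch group: p(1+a) / [1 + pa + (1−p)s]
- Odds ratio: (1−a)(1+s) / [(1−s)(1+a)]

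Example with a = 0.10, s = 0.20: combination 0.585/(0.585 + 0.280) = 67.6%; patch 0.715/(1 + 0.065 + 0.070) = 63.0%; difference +4.6 points; odds ratio (0.90 × 1.20)/(0.80 × 1.10) = 1.23.

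| a / s | Overall stopping | Combination | Patch | Difference (points) | Odds ratio |
|---|---|---|---|---|---|
| 10% / 20% | 13.5% | 67.6% | 63.0% | +4.6 | 1.23 |
| 10% / 30% | 17.0% | 70.5% | 61.1% | +9.4 | 1.52 |
| 20% / 10% | 16.5% | 62.3% | 67.0% | −4.7 | 0.81 |
| 30% / 10% | 23.0% | 59.1% | 68.7% | −9.6 | 0.66 |
| 10% / 10% or 20% / 20% | 10% or 20% | 65.0% | 65.0% | 0 | 1.00 |

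**4. Stoppers excluded.** If they are removed from the combination arm only, the four unequal scenarios give +2.6, +5.5, −2.7 and −5.9 points (the combination column minus 65%). If the same stopping pattern holds in both arms and the exclusion applies to both, both groups have the same expected rate and the bias under no true effect is zero.

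**5. Effect on tests (simulated, complete outcomes, stoppers regrouped).** Figures follow the order of the four unequal scenarios.

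- Unadjusted test, two-sided 5%, 67 per arm: false-positive rates of about 8%, 20%, 9% and 21%.
- The same with 50 per arm: 7.6%, 16.0%, 8.0% and 16.5%.
- One-sided 5% towards the combination, 67 per arm: 13.7%, 29.7%, 1.5% and 0.3%.
- Logistic model adjusted for sex and dependence, two-sided 5%, 67 per arm: about 8%, 19%, 9% and 19–21%, so adjustment does not cure the problem.
- The same logistic model by randomised arm: 4.8% to 5.4%, median odds ratio 1.00.

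**The case against.** **The wording may be loose.** The authors may have meant assigned treatment, or treatment started as allocated; in either case little changes. But item 2 names the randomised group separately and then uses a different term twice, so the text as it stands does not say this. If assignment was meant, the correction is a change of words.

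**These are not the primary analysis.** That stands. The primary contrast is stated by randomised group, an unadjusted test by randomised arm remains valid, and adjusting for the strata adds little: in simulations of 65% against 80%, one-sided power changed by less than 3 points for assumed dependence odds ratios of 1 to 5. The case for the change rests on keeping the adjusted estimate randomised, not on power.

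**The size is assumed.** That stands too. The bias can run either way or vanish. The one-sided results show no excess of false claims of benefit when abstainers stop more often, and the rates are lower at 50 per arm than at 67.

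**Stronger readings that the documents do not support.**

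- A reader might infer that the per-protocol analysis is really an as-treated one. The sentence can equally mean restriction to people who received what they were allocated. What the text supports is that the set is undefined.
- A reader might infer from *treatment granted* that the intention-to-treat analysis itself groups by treatment taken. The next statements tie the outcome to the randomised group, and the Elimination criteria remove nobody after randomisation. The phrase names a second basis for grouping and should go, but it does not show that the primary analysis departs from randomisation.

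**Conclusion.** The point holds for the grouping variable. Followed literally, the plan produces one adjusted estimate of 12-month abstinence, and that estimate is not a comparison of randomised arms. Its bias depends on how *received* is defined and on whether stopping is related to outcome. Under the assumptions shown, it is about +5 to +9 points or −5 to −10 points with regrouping, and zero when stopping is unrelated to outcome. With exclusion, it is zero under no true effect if stopping follows the same pattern in both arms. Confidence is high about the wording and low about the size, since every stopping rate is assumed.

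A reader might also infer that, because the primary contrast is by randomised group, the primary analysis is sound and the main conclusion safe. The documents do not support that. The Abstinence definition lists a positive cotinine as corroboration, while the cotinine entry in the same variable list treats a positive result as active smoking. No rule is given for missing 12-month outcomes despite 25% expected loss. This point does not endorse those parts of the plan, or the sample size.

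**What to change.** 1. Fit the logistic regression in all randomised participants by **randomised arm**, with a fixed covariate list: sex, dependence (low against moderate/severe), age and smoking rate. Replace the open-ended wording that introduces the covariates.
2. State one missing-outcome rule in advance and use it for both the primary and the adjusted analysis. The plan has none at present, so it must be written.
3. Report the adjusted effect with its confidence interval beside the intention-to-treat result.
4. Remove *treatment granted* from the intention-to-treat sentence.
5. Keep any treatment-received or per-protocol analysis as supportive only, with *received* and the analysis set defined for both arms before outcomes are analysed.

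The cost is analysis-plan wording. Arm, sex, age, smoking rate and dependence are already planned variables, so no new data are needed. A per-protocol set built on measured adherence would need data that the visit procedures do not list; this point does not require one.
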